8.6.3 Statistical Methods for Biomarker Analyses

The evaluation of a general positive association between biomarker score and ORR/DCR will be investigated via standard logistic regression as well as generalized additive models. The profiles of PPV (positive predictive value), NPV (negative predictive value), and the percentage of subjects above a given cut-off, along with intervals quantifying the uncertainty in those profiles, will be estimated as a function of potential cut-offs. A biomarker cut-off that maintains high NPV (e.g., near or above 90%) while achieving meaningful enrichment of response and largely capturing subjects showing durable clinical benefit is sought. Receiver operating characteristic curve analysis will also be used to understand the sensitivity and specificity profile and examine cut-offs that might be suggested based on the ROC curve and their appropriateness with regard to PPV and NPV.

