4.1.3 Ongoing Clinical Trials

Subjects with PD-L1 positive mCRPC have been treated with pembrolizumab monotherapy in KN028. As of 24-Jul-2015, 16 subjects with PD-L1 positive mCRPC were enrolled and treated with pembrolizumab monotherapy. All had treatment with prior docetaxel and targeted endocrine therapy. Three confirmed partial responses (PR) were reported for an ORR at that time of 19%. The responses were durable and treatment was well tolerated. This study, KEYNOTE-199 (KN199), has been designed to further evaluate the signal of activity seen in KN028 with pembrolizumab monotherapy.

Ongoing clinical trials are also being conducted in advanced MEL, non-small cell lung cancer (NSCLC), head and neck cancer, urothelial cancer, triple negative breast cancer (TNBC), gastric cancer and hematologic malignancies. For study details please refer to the IB.

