8.5.3 Biomarker Discovery Population

The biomarker discovery population consists of the first 100 subjects with RECIST1.1-measurable disease in Cohorts 1 and 2 who are clinically evaluable, which is defined as any subjects who received at least one dose of study drug and had at least 3 post-baseline scans, or discontinued due to radiographic/clinical progression or death before reaching Week 27.

The biomarker discovery population will be used in this study for the evaluation of the association between biomarker score and clinical efficacy and subsequently to determine a biomarker cut-point (if applicable and necessary). The biomarker discovery population will be excluded from any subsequent validation analyses for any biomarker selected population, if applicable. These subjects will still be included in the general efficacy analyses for combined cohorts and by each cohort irrespective of biomarker status.

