8.7 Interim Analysis

Efficacy and safety data will be monitored over time in this single-arm, open-label, multi-cohort study.

One interim analysis will be conducted in the first 100 subjects with RECIST 1.1-measurable disease by RECIST 1.1 (Cohort 1 and Cohort 2) and all subjects in Cohort 3 at about 27 weeks after the completion of enrollment of all these subjects. Other analyses at the interim analysis will include DOR and safety.

A biomarker analysis is planned at the time of the interim analysis where a subset of subjects (the biomarker discovery population, about 100 subjects from Cohorts 1 and 2, see Section 8.5.3 for details) will be used to explore the association between the biomarker score and clinical efficacy/resistance and also to determine the biomarker cut-point. More subjects may be allocated to the biomarker discovery population, if necessary.

The final analysis of ORR in the population with measurable disease by RECIST 1.1 will be performed after all subjects have been enrolled and all subjects have accumulated mature data and had adequate follow-up. All other analyses, including safety, DOR, DCR, PSA response, time to PSA progression, rPFS, and OS will be analyzed at this time.

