### 3.5.3 Biomarker Discovery Population

The biomarker discovery population consists of the first 100 subjects with RECIST1.1 -measurable disease in Cohorts 1 and 2 who are clinically evaluable, which is defined as any subjects who received at least one dose of study drug and had at least 3 post-baseline scans, or discontinued due to radiographic/clinical progression or death before reaching week 27.

The biomarker discovery population will be used in this study for the evaluation of the association between biomarker score and clinical efficacy and subsequently to determine a biomarker cut-point (if applicable and necessary). The biomarker discovery population will be excluded from any subsequent validation analyses for any biomarker selected population, if applicable. These subjects will still be included in the general efficacy analyses for all cohorts combined and by each cohort irrespective of biomarker status.

More details will be provided in a separate biomarker analysis plan.

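### Does the exploratory biomarker cut-off criterion, with its 90% NPV target and open-ended discovery set, need to change?

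*Protocol*

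**What the plan says.** Protocol 8.6.3 first examines whether biomarker score is positively associated with ORR or DCR, using logistic regression and generalized additive models. PPV, NPV and the share of subjects above each cut-off, "along with intervals quantifying the uncertainty in those profiles, will be estimated as a function of potential cut-offs". The cut-off wanted is one that "maintains high NPV (e.g., near or above 90%) while achieving meaningful enrichment of response and largely capturing subjects showing durable clinical benefit is sought". ROC analysis supplements this. sSAP 3.6.3 has the same text.

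The discovery population (Protocol 8.5.3, sSAP 3.5.3) is the first 100 subjects in Cohorts 1 and 2 with measurable disease who received a dose and either "had at least 3 post-baseline scans, or discontinued due to radiographic/clinical progression or death before reaching Week 27". Determining a cut-point is conditional on its being applicable and necessary. "The biomarker discovery population will be excluded from any subsequent validation analyses for any biomarker selected population, if applicable". sSAP 3.5.3 adds: "More details will be provided in a separate biomarker analysis plan".

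On the interim, Protocol 8.7 says: "One interim analysis will be conducted in the first 100 subjects with RECIST 1.1-measurable disease". On the discovery set it says: "More subjects may be allocated to the biomarker discovery population, if necessary". Protocol 8.2 masks subject-level biomarker results from the study team until database lock for the primary report and restricts access to designated unblinded sponsor staff. Protocol 8.8 states that no hypotheses are tested.

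**The concern.** Three features look weak when read together.

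- **The NPV target.** Of the three parts of the criterion (NPV, enrichment, capture of durable benefit), only NPV has a figure. At an ORR near 10%, a marker with no relation to response already has an expected NPV of 90%. An NPV of 90% could then be read as evidence when it only reflects a low response rate. ORR of 10% is the lowest scenario in Protocol Table 10. The prior data do not rule it out: "Three confirmed partial responses (PR) were reported for an ORR at that time of 19" per cent, from 16 PD-L1 positive subjects.
- **The search.** Intervals are planned at each cut-off, but no allowance is described for choosing the cut-off on the same data. The PPV of a chosen cut-off will tend to be too high.
- **The discovery set.** Membership depends on post-baseline course, so it may differ from the 100 subjects in the interim ORR. It may also be enlarged with no trigger or limit, which would use up subjects otherwise left for validation.

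At stake is a false cut-off, or an overstated one, being carried out of the interim analysis.

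**Working it through.** **Inputs.** NPV target of about 90% (Protocol 8.6.3); discovery n = 100 (8.5.3); about 200 subjects in Cohorts 1 and 2 and ORR scenarios of 10% to 30% (8.9); prior response 3/16 (4.1.3).

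**1. The plan's own figure.** Table 10, 10 responders in 100: the exact (Clopper-Pearson) interval is 4.90% to 17.62%, width 12.72%. The table gives 4.9% to 17.6% and 12.7%. The other 14 rows also reproduce to rounding. For 3/16 the exact interval is 4.0% to 45.6%, so 10% is not excluded.

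**2. What NPV measures.** Let π be the ORR, q the marker-positive fraction and s the share of responders who are positive. Then PPV = πs/q and NPV = 1 − π(1 − s)/(1 − q).

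- Useless marker (s = q): NPV = 1 − π, which is 90% at π = 10%, 85% at 15% and 81% at 19%.
- Required s for NPV of 90% at q = 0.5: s = 1 − 0.05/π, which is 0.50 at π = 10% (chance level), 0.67 at 15% and 0.74 at 19%.
- With exactly 10 responders in 100 and a median split, a useless marker reaches NPV ≥ 90% with probability 0.63 (hypergeometric). With 20 responders the probability is 0.01.

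Taken alone, the target says little near 10% and discriminates at 19% to 20%.

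**3. What enrichment adds.** Since π = q·PPV + (1 − q)(1 − NPV), PPV > π holds exactly when NPV > 1 − π. Setting NPV against 1 − ORR therefore repeats the enrichment requirement. For example, 1.5-fold enrichment at q = 0.5 means s = 0.75 and NPV = 1 − 0.5π, which is 95% at π = 10% and 90.5% at 19%.

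**4. Searching with a useless marker** (simulated, n = 100, cut-offs at ranks 20 to 80).

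- NPV ≥ 90% alone, ORR 10%: some cut-off qualifies in about 84% to 85% of runs. Taking the highest qualifying PPV gives a mean of 14.0% against a true 10% (14.9% if the responder count is fixed at 10). The unadjusted 95% interval for PPV covers the truth 94% of the time.
- All three parts, with enrichment set at 1.5-fold and capture at 70% (both assumed): 12% of runs at ORR 10%, 5% at 15%, 2% at 19%. Varying these over 1.25- to 2-fold and 60% to 80% gives 1.5% to 41%, 0.2% to 24% and 0% to 13%.
- With an association step added first (assumed one-sided 5% rank test; the plan gives no threshold): 12.4% falls to 4.3%, 5.5% to 3.0% and 2.4% to 1.5%.
- If NPV refers to an outcome with a rate of 25% or 30% (assumed, as DCR might be), the three-part rule passes in 0.5% or 0.1% of runs with no association step.

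**5. Validation in separate subjects.** A cut-off falsely selected by the three-part rule at ORR 10% passes again in 4% of cases with 100 validation subjects and in 11% with 50. Overall: 0.12 × 0.04 ≈ 0.5% and 0.12 × 0.11 ≈ 1.3%.

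**6. Evaluability.** If 10 to 20 non-responders in 100 were not evaluable (assumed), ORR in the set moves from 10% to 10/90 = 11.1% or 10/80 = 12.5%. Useless-marker NPV drops to 88.9% or 87.5%, so 90% becomes slightly harder to reach.

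**The case for a change.** The best case for changing the plan is that the interim is meant to determine the cut-point, while enrichment and capture have no numbers. The rule's error rate therefore cannot be known, as the 1.5% to 41% spread at ORR 10% shows. When the three-part rule picks a useless marker at ORR 10%, mean PPV is 15.4%, apparent enrichment is 1.85-fold against a true 1.0, and an unadjusted interval covers the true rate only 87% of the time. Separate validation is the main protection, and open-ended enlargement erodes it. With 150 of about 200 subjects in discovery, a validated PPV of 20% in a half-positive group has an interval of 6.8% to 40.7% (5/25) instead of 10.0% to 33.7% (10/50). Masking does not stop the unblinded staff from enlarging the set after seeing results.

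All of this arithmetic stands, and a scan-chosen PPV is indeed optimistic by 4 to 5 percentage points at ORR 10%. But the 87% applies only to markers already falsely selected. The wide spread comes from thresholds supplied for the check, since the plan states an aim with an example figure and not a decision rule. The protocol (8.0 and 8.6) and the sSAP (1 and 3.5.3) assign the detail to a separate biomarker analysis plan, where numerical thresholds, a resampling method and an enlargement rule would naturally sit.

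The argument about the two sets of 100 does not stand. Nothing in the plan compares PPV or NPV with the interim ORR, and the response rate in the discovery set itself is always to hand. Counting under-scanned subjects as non-responders would raise useless-marker NPV back to 90%, so it would loosen the criterion.

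**Conclusion.** No change is needed. The NPV figure is uninformative by itself only if NPV is defined on objective response and ORR is near 10%. The enrichment requirement covers that case, and at the prior 19%, or for a more frequent outcome such as DCR, the target does discriminate. Optimism from the search is real but modest. The plan already keeps discovery subjects out of validation and masks biomarker results from the study team. On the simulated assumptions a useless marker survives both stages in 0.5% to 1.3% of cases at ORR 10%, before any credit for the association analysis.

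The thresholds, the search range and the rank test are assumptions made for this check, and the contents of the separate biomarker plan are unknown. What is left is missing detail in an exploratory analysis that a competent analyst would settle there: which outcome defines NPV, PPV and NPV shown beside the response rate in the same set, an estimate for the chosen cut-off that allows for the search, and any enlargement decided without sight of biomarker-by-outcome results. The primary ORR estimates do not depend on any of it.

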8.6.4 Summaries of Baseline Characteristics, Demographics, and Other Analyses

The number and percentage of subjects screened, enrolled, the primary reasons for screening failure, and the primary reason for discontinuation will be displayed. Demographic variables, baseline characteristics, primary and secondary diagnoses, and prior and concomitant therapies will be summarized by treatment either by descriptive statistics or categorical tables.

8.7 Interim Analysis

Efficacy and safety data will be monitored over time in this single-arm, open-label, multi-cohort study.

One interim analysis will be conducted in the first 100 subjects with RECIST 1.1-measurable disease by RECIST 1.1 (Cohort 1 and Cohort 2) and all subjects in Cohort 3 at about 27 weeks after the completion of enrollment of all these subjects. Other analyses at the interim analysis will include DOR and safety.

A biomarker analysis is planned at the time of the interim analysis where a subset of subjects (the biomarker discovery population, about 100 subjects from Cohorts 1 and 2, see Section 8.5.3 for details) will be used to explore the association between the biomarker score and clinical efficacy/resistance and also to determine the biomarker cut-point. More subjects may be allocated to the biomarker discovery population, if necessary.

The final analysis of ORR in the population with measurable disease by RECIST 1.1 will be performed after all subjects have been enrolled and all subjects have accumulated mature data and had adequate follow-up. All other analyses, including safety, DOR, DCR, PSA response, time to PSA progression, rPFS, and OS will be analyzed at this time.

8.8 Multiplicity

There will be no hypothesis testing performed in this study. For the primary and secondary objectives in this Phase II study, no adjustment to control for Type I error is planned.

8.9 Sample Size and Power Calculations

The primary objective of this study is to estimate ORR in Cohorts 1 and 2 combined, Cohort 1, Cohort 2, and Cohort 4. The planned sample size is approximately 370 with about 200 subjects in Cohorts 1 and 2, 50 subjects in Cohort 3, 80 subjects in Cohort 4, and 40 subjects in Cohort 5. With a sample size of 200, 100, and 80, the confidence intervals for an observed response rate of 10%, 15%, 20%, 25% and 30% are listed below for 95% confidence level (Table 10). In addition, about 50 subjects with bone-predominant disease at baseline for Cohort 3 will be enrolled.

Table 10 Confidence Intervals for Different Observed Response Rates and Sample Size

Sample Size	Number of Subjects with a response	Observed Response Rate	95% CI	95% CI Width
200	20	10%	(6.2%, 15.0%)	8.8%
200	30	15%	(10.4%, 20.7%)	10.4%
200	40	20%	(14.7%, 26.2%)	11.5%
200	50	25%	(19.2%, 31.6%)	12.4%
200	60	30%	(23.7%, 36.9%)	13.1%
100	10	10%	(4.9%, 17.6%)	12.7%
100	15	15%	(8.6%, 23.5%)	14.9%
100	20	20%	(12.7%, 29.2%)	16.5%
100	25	25%	(16.9%, 34.7%)	17.8%
100	30	30%	(21.2%, 40.0%)	18.7%
80	8	10%	(4.4%, 18.8 %)	14.3%
80	12	15%	(8.0%, 24.7 %)	16.7%
80	16	20%	(11.9%, 30.4 %)	18.6%
80	20	25%	(16.0%, 35.9 %)	19.9%
80	24	30%	(20.3%, 41.3 %)	21.0%

8.10 Subgroup Analyses and Effect of Baseline Factors

For the primary objective ORR, subgroup analyses to be performed include but may not be limited to following subgroups based on

- Age (<65 years, ≥65 years)
- Race
- PD-L1 expression level (positive, negative),
- And biomarker status as appropriate
- RECIST-measurability (yes, no)

Categories of subgroup may be subject to change according to actual data. Categories with few than 5 subjects might not be considered or might be combined into other categories.

8.11 Extent of Exposure

Extent of Exposure for a subject is defined as number of cycles in which the subject receives the study medication infusion. Summary statistics will be provided on Extent of Exposure for ASaT population.

9.0 LABELING, PACKAGING, STORAGE AND RETURN OF CLINICAL SUPPLIES

9.1 Investigational Product

The investigator shall take responsibility for and shall take all steps to maintain appropriate records and ensure appropriate supply, storage, handling, distribution and usage of investigational product in accordance with the protocol and any applicable laws and regulations.

Clinical Supplies will be provided by the Sponsor as summarized in [Table 11](#).

Clinical supplies will be packaged to support enrollment and replacement subjects as required. When a replacement subject is required, the Sponsor or designee needs to be contacted prior to dosing the replacement supplies.

Table 11 Product Description

Product Name & Potency	Dosage Form	Source/Additional Information
Pembrolizumab (MK-3475) 50 mg	Lyophilized powder for IV infusion	Provided centrally by the Sponsor.
Pembrolizumab (MK-3475) 100 mg/4 mL (25 mg/mL)	Solution for IV infusion	Provided centrally by the Sponsor

All supplies indicated in [Table 11](#) will be provided per the “Source/Additional Information” column depending on local country operational requirements.

Any commercially available product not included in [Table 11](#) will be provided by the trial site, subsidiary or designee. Every attempt should be made to source these supplies from a single lot/batch number. The trial site is responsible for recording the lot number, manufacturer, and expiry date for any locally purchased product as per local guidelines unless otherwise instructed by the Sponsor.

9.2 Packaging and Labeling Information

Clinical supplies will be affixed with a clinical label in accordance with regulatory requirements.

Subjects will receive open label pembrolizumab (MK-3475), supplied either as vials containing 50 mg of lyophilized powder, or as kits containing 2 vials of solution for infusion.

9.3 Clinical Supplies Disclosure

This trial is open-label; therefore, the subject, the trial site personnel, the Sponsor and/or designee are not blinded. Treatment (name, strength or potency) is included in the label text; random code/disclosure envelopes or lists are not provided.

9.4 Storage and Handling Requirements

Clinical supplies must be stored in a secure, limited-access location under the storage conditions specified on the label.

Receipt and dispensing of trial medication must be recorded by an authorized person at the trial site.

Clinical supplies may not be used for any purpose other than that stated in the protocol.

9.5 Discard/Destruction>Returns and Reconciliation

The investigator is responsible for keeping accurate records of the clinical supplies received from the Sponsor or designee, the amount dispensed to and returned by the subjects and the amount remaining at the conclusion of the trial. For all trial sites, the local country Sponsor personnel or designee will provide appropriate documentation that must be completed for drug accountability and return, or local discard and destruction if appropriate. Where local discard and destruction is appropriate, the investigator is responsible for ensuring that a local discard/destruction procedure is documented.

9.6 Standard Policies

Trial site personnel will have access to a central electronic treatment allocation/randomization system (IVRS/IWRS system) to allocate subjects, to assign treatment to subjects and to manage the distribution of clinical supplies. Each person accessing the IVRS system must be assigned an individual unique PIN. They must use only their assigned PIN to access the system, and they must not share their assigned PIN with anyone.

10.0 ADMINISTRATIVE AND REGULATORY DETAILS

10.1 Confidentiality

10.1.1 Confidentiality of Data

By signing this protocol, the investigator affirms to the Sponsor that information furnished to the investigator by the Sponsor will be maintained in confidence, and such information will be divulged to the institutional review board, ethics review committee (IRB/ERC) or similar or expert committee; affiliated institution and employees, only under an appropriate understanding of confidentiality with such board or committee, affiliated institution and employees. Data generated by this trial will be considered confidential by the investigator, except to the extent that it is included in a publication as provided in the Publications section of this protocol.

10.1.2 Confidentiality of Subject Records

By signing this protocol, the investigator agrees that the Sponsor (or Sponsor representative), IRB/ERC, or regulatory authority representatives may consult and/or copy trial documents in order to verify worksheet/case report form data. By signing the consent form, the subject agrees to this process. If trial documents will be photocopied during the process of verifying worksheet/case report form information, the subject will be identified by unique code only; full names/initials will be masked prior to transmission to the Sponsor.

By signing this protocol, the investigator agrees to treat all subject data used and disclosed in connection with this trial in accordance with all applicable privacy laws, rules and regulations.

10.1.3 Confidentiality of Investigator Information

By signing this protocol, the investigator recognizes that certain personal identifying information with respect to the investigator, and all subinvestigators and trial site personnel, may be used and disclosed for trial management purposes, as part of a regulatory submissions, and as required by law. This information may include:

1. name, address, telephone number and e-mail address;
2. hospital or clinic address and telephone number;
3. curriculum vitae or other summary of qualifications and credentials; and
4. other professional documentation.

Consistent with the purposes described above, this information may be transmitted to the Sponsor, and subsidiaries, affiliates and agents of the Sponsor, in your country and other countries, including countries that do not have laws protecting such information. Additionally, the investigator's name and business contact information may be included when reporting certain serious adverse events to regulatory authorities or to other investigators. By signing this protocol, the investigator expressly consents to these uses and disclosures.

If this is a multicenter trial, in order to facilitate contact between investigators, the Sponsor may share an investigator's name and contact information with other participating investigators upon request.

